RT-PCR	Reverse Transcription Polymerase Chain Reaction
RT-qPCR	Reverse Transcription-quantitative Polymerase Chain Reaction
SAE	Serious Adverse Event

SAP	Statistical Analysis Plan
SARS-CoV-2	Severe Acute Respiratory Syndrome Coronavirus 2
SAS	Statistical Analysis System
SD	Standard Deviation
SE	Standard Error
SI	System International
SoC	Standard of Care
SOC	System Organ Class
SpO ₂	Saturation Peripheral Oxygen
SUSAR	Suspected Unexpected Serious Adverse Reactions
TEAE	Treatment-emergent Adverse Event
TEAESI	Treatment-emergent Adverse Events of Special Interest
TESAE	Treatment-emergent Serious Adverse Event
TLF	Table, Listing and Figure
ULN	Upper Limit of Normal
WHO	World Health Organization

1. ADMINISTRATIVE STRUCTURE

This study is being conducted under the sponsorship of CELLTRION, Inc. (hereinafter referred to as “CELLTRION”). The clinical monitoring, medical writing and bioanalytical lab analysis are being performed under contract with [REDACTED] in collaboration with CELLTRION. Virology analysis is being performed under contract with [REDACTED] in collaboration with CELLTRION. Randomization is being performed under contract with [REDACTED], in collaboration with CELLTRION. The data management and statistical analysis are being performed by CELLTRION.

2. INTRODUCTION

This statistical analysis plan (SAP) defines the statistical methods and data presentations to be used by CELLTRION Clinical Statistics team in the analysis and presentation of data for Part 2 of CELLTRION study number CT-P59 3.2, entitled as “A Phase 2/3, Randomized, Parallel-group, Placebo-controlled, Double-Blind Study to Evaluate the Efficacy and Safety of CT-P59 in Combination with Standard of Care in Outpatients with Severe Acute Respiratory Syndrome Coronavirus (SARS-CoV-2) Infection”.

Two clinical study reports (CSRs) will be generated during entire study period of Part 2 as follows:

- Clinical study report with available data up to and including Day 28 in Part 2. The following data will be included.

	Ongoing at Day 28	Withdrawal prior to Day 28
Scheduled Visit (including EOT)	Up to and including Day 28 for each patient	All available data
Unscheduled Visit	On or before Day 28 visit date for each patient	All available data up to the latest date of the all patient’s Day 28 visit date.
Non-visit based data (e.g. adverse events and medications)	All available data having a start date or imputed start date on or before Day 28 visit date for each patient.	

- Clinical study report with all data after completion of Part 2

If additional CSRs are required for regulatory or academic purposes, CSRs will be generated after the first database lock and unblinding process.

This SAP covers all specified analysis for Part 2 and is based on the following documents:

- Study Protocol Version 7.0 – 30th April 2021

- Unique CRF for Version 3.0 – 23th October 2020

3. STUDY OBJECTIVES

Primary, key secondary, secondary and exploratory objectives are described as below.

3.1. Primary Objective

The primary objective of this study for Part 2 is as follows:

- To demonstrate the clinically meaningful therapeutic efficacy of CT-P59 as determined by proportion of patients with clinical symptom requiring hospitalization, oxygen therapy, or experiencing mortality due to SARS-CoV-2 infection up to Day 28 in high-risk patients

Details of definition of ‘requiring hospitalization due to SARS-CoV-2 infection’, ‘requiring oxygen therapy due to SARS-CoV-2 infection’ and ‘experiencing mortality due to SARS-CoV-2 infection’ for statistical analyses are described in [Section 9.1](#).

“High-risk patients” are defined as patients who are at high risk for progressing to severe COVID-19 and/or hospitalization and who meet at least one of the following criteria (high-risk criteria):

- Advanced age (Age >50 years)
- Obesity (Body Mass Index [BMI] >30 kg/m²)
- Cardiovascular disease, including hypertension
- Chronic lung disease, including asthma
- Type 1 or type 2 diabetes mellitus
- Chronic kidney disease, including those on dialysis
- Chronic liver disease
- Immunosuppressed, based on prescriber’s assessment. Examples include: cancer treatment, bone marrow or organ transplantation, immune deficiencies, HIV (if poorly controlled or evidence of acquired immune deficiency syndrome), sickle cell anemia, thalassemia, and prolonged use of immune weakening medications.

For the criteria other than advanced age and obesity, a detailed terminology for each criterion will be confirmed by medical reviewers and a list of high-risk patients will be confirmed before unblinding.

3.2. Key Secondary Objectives

The key secondary objectives of this study for Part 2 are as follows:

- To demonstrate the clinically meaningful therapeutic efficacy of CT-P59 as determined by proportion of patients with clinical symptom requiring hospitalization, oxygen therapy, or experiencing mortality due to SARS-CoV-2 infection up to Day 28 in all randomized patients
- To assess the potential therapeutic efficacy of CT-P59 as determined by time to clinical recovery up to Day 14 in high-risk patients
- To assess the potential therapeutic efficacy of CT-P59 as determined by time to clinical recovery up to Day 14 in all randomized patients

Definition of clinical recovery and the time to clinical recovery is described in [Section 9.2](#).

3.3. Secondary Objective

The secondary objectives of this study for Part 2 are as follows:

- To evaluate the additional efficacy of CT-P59
- To evaluate overall safety of CT-P59, including immunogenicity and potential effects on the incidence of antibody-dependent enhancement (ADE)

3.4. Exploratory Objective

The exploratory objectives of this study for Part 2 are as follows:

- To assess the viral efficacy, genotype and phenotype of SARS-CoV-2 viral isolates
- To assess the serology of SARS-CoV-2 antibody

4. INVESTIGATIONAL PLAN

4.1. Overall Study Design and Plan

Part 2 of this study is a phase 3, randomized, parallel-group, placebo-controlled, double-blind study to evaluate the efficacy, safety, virology of CT-P59 in combination with Standard of Care (SoC) (except potential antiviral drugs and/or possible anti-SARS-CoV-2 activity drugs) in outpatients with mild to moderate symptoms of SARS-CoV-2 infection, not requiring supplemental oxygen therapy. ‘Outpatient’ in this study includes patients visiting the study center, and patients confined in the study center or quarantine at home due to local regulation or at discretion of the investigator.

[figure not shown]
In Part 2, approximately 1300 patients will be randomly assigned in a 1:1 ratio to CT-P59

40 mg/kg or placebo.

The study will be unblinded to the predefined unblinded teams of sponsor and Contract Research Organization (CRO) for reporting purposes after completion of the Day 28 assessments of the last enrolled patient in Part 2. However, the treatment assignment will remain blinded to the investigators, all designated study staff (with the exception of the unblinded study pharmacists or unblinded staff designated to prepare the study drug for infusion), and patients until the final CSR is generated.

The overview of study design for Part 2 is illustrated in [Figure 1](#).

Figure 1. Schematic Diagram of Study Patients for Part 2

Note: In Part 2, patients with body weight at or above 200 kg will receive 8,000 mg of CT-P59 or matching volume of placebo.

1. Of 1300 patients in Part 2, 822 high-risk patients will be included based on the sample size calculation.

The study will comprise of 3 study periods (including Screening, Treatment Period and Follow-up Period). An End-of-Treatment (EOT) visit will occur on Day 90 and the total study duration is planned as 180 days for each patient. The overview of the study is presented in [Figure 3](#).

Screening (Day-7 to 1): Screening will take place between Days –7 and 1, prior to the study drug administration. No study procedures will be performed prior to informing the patient about the study and obtaining written informed consent form (ICF). It is critical that patients receive study drug no more than 7 days from the onset of symptoms.

[figure not shown]
Screening evaluations will be completed prior to the randomization on Day 1. Outpatients with mild to moderate symptoms of SARS-CoV-2 infection not requiring supplemental oxygen therapy will be eligible for enrollment. Patients must have a local confirmation of SARS-CoV-2 infection by positive test result from a sponsor-supplied rapid SARS-CoV-2 diagnostic test or reverse transcription polymerase chain reaction (RT-PCR). If the patient had a RT-PCR result (sample collected within 72 hours prior to the study drug administration) confirming SARS-CoV-2 infection even if before signing the ICF, the

patient can be enrolled without additional confirmation of SARS-CoV-2 infection at Screening.

If Screening visit date and the date of study drug administration (Day 1) are the same, all assessments scheduled for the Screening and Day 1 visit can be performed only once on the same day before randomization.

During the Screening Period, only one re-test for confirmation of SARS-CoV-2 infection will be allowed, if study drug can be administered no more than 7 days from onset of symptom based on the re-test result. The enrollment process is presented in [Figure 2](#).

Figure 2. Enrollment Process

1. Must be locally done by a sponsor-supplied rapid SARS-CoV-2 diagnostic test or RT-PCR. If the patient has a RT-PCR result (sample collected within 72 hours prior to the study drug administration) confirming SARS-CoV-2 infection even if before signing the ICF, the patient can be enrolled without additional confirmation of SARS-CoV-2 infection at Screening.
2. During the Screening Period, only one re-test for confirmation of SARS-CoV-2 infection will be allowed, if study drug can be administered no more than 7 days from onset of symptom based on the re-test result.

Abbreviation: RT-PCR = reverse transcription polymerase chain reaction; SARS-CoV-2 = severe acute respiratory syndrome coronavirus 2.

Treatment Period (Day 1 to prior to End-of-Treatment Visit): In the Treatment Period, the patients who meet all of the inclusion criteria and none of the exclusion criteria will be randomized on Day 1. If it is concluded that the patients are not eligible in Day 1 assessments before randomization, the patients will be considered as screening failure even if he/she was eligible based on assessments results performed during Screening Period.

Approximately 1300 patients will be randomly assigned in a 1:1 ratio (650 patients, respectively) to receive either a single dose of CT-P59 40 mg/kg, or placebo on Day 1. All patients will be given optimal SoC (except potential antiviral drugs and/or possible anti-SARS-CoV-2 activity drugs).

Randomization will be stratified by age (≥ 60 years vs. < 60 years), baseline comorbidities (Yes vs. No, having at least one of cardiovascular disease, chronic respiratory disease, hypertension, diabetes mellitus, and pneumonia) and region (United States vs. Asia vs. European Union vs. other) in Part 2.

[figure not shown]
All enrolled patients in the study will complete the study visits during the treatment period either by visiting the study center, confinement in the study center, or home visiting services by health care professionals, whichever applicable according to the local regulation or at discretion of investigator.

Patients will comply with all appropriate visits and assessments. If a patient withdraws prematurely after the study drug administration, the patient will be asked to return to the study site on the next scheduled visit for the EOT assessments.

Follow-Up Period (From End-of-Treatment Visit to Day 180): For all patients including patients who withdraw prematurely after the study drug administration, each telephone call follow-up will occur biweekly from EOT visit up to Day 180. During the Follow-up Period, patients will be asked if they have any SARS-CoV-2 infection related signs and symptoms by telephone calls to capture the suspicious ADE occurrence.

The schedule of assessments is presented in [Appendix 1](#).

Figure 3. Study Design Scheme for Part 2

Abbreviations: SARS-CoV-2 = severe acute respiratory syndrome coronavirus 2; SoC = standard of care; RT-qPCR = reverse transcription quantitative polymerase chain reaction.

Notes: a) In Part 2, patients with body weight at or above 200 kg will receive 8,000 mg of CT-P59 or matching volume of placebo. b) Of 1300 patients in Part 2, 822 high-risk patients will be included based on the sample size calculation.

5. GENERAL STATISTICAL CONSIDERATIONS

Continuous data will be summarized using descriptive statistics: number of patients (n), mean, standard deviation (SD), minimum, median and maximum unless otherwise specified. The descriptive statistics will be calculated using raw data before rounding although rounded values are listed. The following rules will be followed with regard to the number of decimal places:

- Minimum and maximum will be displayed without rounding from values in the source listing.
- Mean and median will be rounded to one more decimal place than the maximum decimal place of values in the source listing.
- Standard deviation and standard error (SE) will be rounded to one more decimal place than mean.
- Point estimate and confidence interval (CI) obtained from statistical procedures will be displayed to two decimal places.
- P-value obtained from statistical procedures will be displayed to four decimal places if the value is greater than 0.0001, otherwise <.0001.

Categorical data will be summarized in a frequency table showing the numbers and percentages of patients. Percentages and corresponding CIs will be rounded to one decimal place and will be suppressed when the count is zero. P-value will be displayed using the same rule as continuous data. The denominator for all percentages will be the number of patients within each treatment group for the population of interest, unless otherwise specified.

Unscheduled and EOT visit will not be summarized in visit-based tables, unless otherwise specified. But, all data will be displayed in listings. Unless otherwise specified, listings will be sorted by the treatment group, patient number, and visit, if applicable. In cases where more ordering is required, other variables will be included in the sort order as applicable.

For the purpose of summarization, any numeric values recorded below the lower limit or above the upper limit of quantification will be set to the respective limit for all related summaries. In listings, original results containing inequality sign will be displayed, unless otherwise specified.

5.1. Software

All analyses will be conducted using [REDACTED]

5.2. Sample Size

In Part 2, to demonstrate the efficacy of CT-P59 40 mg/kg compared to placebo by proportion of patients with clinical symptoms requiring hospitalization, oxygen therapy, or experiencing mortality due to SARS-CoV-2 infection up to Day 28 in high-risk patients, a total of 822 high-risk patients (411 patients per group) will provide 80% power to detect 4.2% difference (60% reduction) at a significance level of 5% (2-sided test) assuming placebo rate of 7.1% and CT-P59 rate of 2.9%. As it is expected that high-risk patients will account for 64% of all patients, approximately a total of 1300 (650 patients per group) patients will be enrolled to this study.

Approximately, a total of 1300 (for high-risk patients, 822) patients will provide following statistical power for the key secondary endpoints at the 2-sided significance level of 5%:

- At least 80% power for proportion of patients with clinical symptom requiring hospitalization, oxygen therapy, or experiencing mortality due to SARS-CoV-2 infection up to Day 28 in all randomized patients, assuming placebo rate of 5.5% and CT-P59 rate of 2.5% (3% difference [55% reduction])
- At least 90% power for time to clinical recovery up to Day 14 in high-risk patients, assuming 90% of patients with clinical symptoms at baseline for analysis and clinical recovery ratio of 1.5 with 66% of patients achieving clinical recovery
- At least 90% power for time to clinical recovery up to Day 14 in all randomized patients, assuming 90% of patients with clinical symptoms at baseline for analysis and clinical recovery ratio of 1.35 with 65% of patients achieving clinical recovery

5.3. Randomization, Stratification, and Blinding

On Day 1, eligible patients will be randomly assigned in a 1:1 ratio to receive either a single dose of CT-P59 40 mg/kg or placebo.

An Interactive Web Response System (IWRS) will be used for the randomization. Unblinded biostatisticians will generate the randomization schedule for IWRS, which will link sequential patient randomization numbers to treatment codes. The randomization numbers will be blocked, and within each block the pre-specified ratio of patients will be allocated to each treatment group. The block size will not be revealed.

Randomization will be stratified by age (≥ 60 years vs. < 60 years), baseline comorbidities (Yes vs. No, having at least one of cardiovascular disease, chronic respiratory disease, hypertension, diabetes mellitus, and pneumonia) and region (United States vs. Asia vs. European Union vs. other) in Part 2.

This study will be double-blind, and will remain blinded to the investigator, all designated study staff (with the exception of the unblinded study pharmacists or unblinded staffs designated to prepare the study drug for infusion and predefined unblinded teams in the sponsor and CRO), and patients until the final CSR is generated.

Under normal circumstances, the blind should not be broken. The blind should be broken only if specific emergency treatment would be dictated as knowing the study drug assignment is required for medical management or regulatory requirement (e.g., for serious adverse event [SAE] and death). In such cases, the investigator may, in an emergency, determine the identity of the study drug by using the applicable procedure.

The date, time and reason for the unblinding must be documented in the source document and appropriate field of the eCRF, and the medical monitor will be informed as soon as possible. All unblinding events will be recorded and reported to the medical monitor and the sponsor. Any patients for whom the blind is broken may continue in the study at the investigator's discretion. Suspected unexpected serious adverse reactions (SUSAR), which are subject to expedited reporting, should be unblinded before submission to the regulatory authorities if required.

The DSMB and the statistician(s) who provide the safety analyses for the DSMB will also be unblinded upon request from DSMB members during closed session. The overall randomization code will be broken only for reporting purposes. This will occur after database lock for data up to Day 28 of the last enrolled patient in Part 2. The unblinded personnel will be predefined and documented before performing the analyses.

5.4. Analysis Sets

The following patient analysis sets are defined: Intent-to-Treat (ITT) Set, ITT Set – High Risk, Intent-to-Treat Infected (ITTI) Set, ITTI Set – High Risk and Safety Set.

Analysis of the ITT Set, ITT Set – High Risk, ITTI Set and ITTI Set – High Risk will be performed according to the treatment they were randomized to. The Safety Set will be analyzed according to actual treatment group. The actual treatment group will be assigned according to their actual treatment, not according to the randomized group, even if there is a discrepancy between the actual treatment administered and the randomized group.

For analysis of time to event endpoints, the following patients will be included in the analysis set:

- Time to clinical recovery: Patients who report at least one symptom at baseline
- Time to negative conversion: Patients who have positive result confirmed based on the negative threshold (as defined in [Section 11.1.1](#)) in the analysis at baseline (or Day 2/Day 3). The same analysis set will be used for the proportion of negative conversion.
- Time to NEWS2 of 0: Patients who have NEWS2 > 0 at baseline

The number of patients in each analysis set will be tabulated by the treatment group. A listing will also be produced displaying data on ITT Set, unless otherwise specified.

5.4.1. Intent-to-Treat Set

The ITT Set is defined as all randomly assigned patients to study drug. All patients assigned randomization ID according to the “Randomization” page of the eCRF will be included.

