5.4.5. Safety Set

The Safety Set is defined as all randomly assigned patients who receive a complete or partial dose of study drug.

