5.5. Definition of Baseline

The baseline value will be considered to be the last non-missing value before the study drug administration. Post-baseline values will be considered to be all values collected after the study drug administration.

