For time to event endpoints (the second and third key secondary endpoints), Kaplan-Meier methodology will be used to estimate the 25th percentile, 50th percentile (median) and 75th percentile in each treatment arm. The Brookmeyer-Crowley methodology (via log-log transformation) will be used to construct the 95% CI for each percentile. The treatment difference will be assessed by the stratified log-rank test presenting p-value. Hazard ratio between two treatment groups and associated 95% CI will be estimated using the stratified Cox proportional hazard model. Since clinical recovery is beneficial outcome, not hazard, the hazard ratio will be expressed as recovery rate ratio.

For time to clinical recovery endpoints, patients who report at least one symptom at baseline will be included in the analysis.

Clinical recovery is defined as all symptoms on the SARS-CoV-2 Infection Symptom Checklist 1 being recorded as 'absent' or 'mild' in intensity for both at least 48 hours. To meet the clinical recovery, all symptoms of SARS-CoV-2 Infection Symptom Checklist 1 defined in [Table 2](#) should satisfy one of the following conditions.

- ✓ Symptoms 'severe' or 'moderate' in intensity at baseline should be changed to 'mild' or 'absent' after the study drug administration for at least 48 hours.
- ✓ Symptoms 'mild' in intensity at baseline should be changed to 'absent' after the study drug administration for at least 48 hours.
- ✓ Symptoms 'absent' in intensity at baseline should maintain as 'absent' for at least 48 hours.
- ✓ Symptoms 'absent' in intensity at baseline becomes 'severe', 'moderate', or 'mild' during the study and changes back to 'absent' for at least 48 hours.
- ✓ Missing symptoms at baseline becomes 'absent' for at least 48 hours.

Patients who meet the clinical recovery criteria for at least two consecutive time points at each symptom will be considered as satisfying condition of 48 hours and achieving clinical

recovery at the first time point. The checklist at Screening or on Day 1 will be used to determine baseline and checklist from Day 2 will be used to determine clinical recovery. If the checklist from Day 2 is recorded twice a day, evening diary will be used to determine clinical recovery. From Day 2, missing time in SARS-CoV-2 Infection Symptom Checklist 1 will be imputed as 10PM for calculation of time to recovery.

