Time to clinical recovery is defined as the elapsed time (in days) from the study drug administration to the earliest day satisfying condition for clinical recovery, and calculated as (Date/time of event or censoring – Date/time of study drug administration). The following patients will be considered censored at their scheduled visit of interest (Day 14).

- Patients who are ongoing in the study without event
- Patients with death or early withdrawal for any reason prior to their scheduled visit of interest (Day 14)
- Patients who administered the rescue therapy due to SARS Cov-2 infection (as defined in [Section 9.3](#)) prior to their scheduled visit of interest (Day 14)
- Patients who were hospitalized due to SARS-CoV-2 infection (as defined in [Section 9.1](#)) prior to their scheduled visit of interest (Day 14)

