9.3. Other Secondary Efficacy Endpoints

The following secondary efficacy endpoints will be assessed up to Day 14 and up to Day 28, unless otherwise specified:

- Proportion of patients requiring supplemental oxygen due to SARS-CoV-2 infection (after study drug administration)
- Proportion of patients with intensive care unit transfer due to SARS-CoV-2 infection (after study drug administration)
- Proportion of patients with all-cause mortality (after study drug administration)
- Time to clinical recovery (after study drug administration)
- Duration of fever defined as the last day in the patient diary on which the temperature >38 °C (100.4 °F) is recorded, or a potentially antipyretic drug (acetaminophen or ibuprofen) is taken.
 - Duration of fever will be calculated for patients with the temperature >38 °C (100.4 °F) or a potentially antipyretic drug on or before study drug administration.
 - A potential antipyretic drug (including but not limited to acetaminophen, paracetamol or ibuprofen) will be identified by medical review.

- Proportion of patients with hospital admission due to SARS-CoV-2 infection (after study drug administration)
- Proportion of patients with mechanical ventilation due to SARS-CoV-2 infection (after study drug administration)
- Proportion of patients requiring rescue therapy due to SARS-CoV-2 infection (after study drug administration)
 - Rescue therapy is defined as prohibited therapy on or after the study drug administration on Day 1.
 - A prohibited therapy due to SARS-CoV-2 infection (including but not limited to remdesivir, chloroquine, hydroxychloroquine, dexamethasone [alternative corticosteroids to dexamethasone], interferon beta-1b, ribavirin, lopinavir-ritonavir, human intravenous immunoglobulin, convalescent plasma, tocilizumab, sarilumab, SARS-CoV-2 vaccine) will be identified by medical review before unblinding.
- Proportion of patient with negative conversion in nasopharyngeal swab specimen based on RT-qPCR at each visit (after study drug administration)
 - Patients who have negative result for at least two consecutive time points will be considered as satisfying negative conversion at the first time point. The two consecutive time points will be determined excluding missing data. If patients who have one negative result followed by all missing results will also be considered as satisfying negative conversion.

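### Randomised patients who are never dosed stay in the ITT Set, but SAP 9.2 gives them no recovery time and five SAP 9.3 endpoints cannot count their events

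*SAP*

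**What the plan says.** **Who is in the set.** SAP 5.4.1 opens with "The ITT Set is defined as all randomly assigned patients to study drug". Dosing is not required; the section goes on to specify that "All patients assigned randomization ID according to the “Randomization” page of the eCRF will be included". By contrast, SAP 5.4.5 says "The Safety Set is defined as all randomly assigned patients who receive a complete or partial dose of study drug", and the ITTI Set in 5.4.3 also needs a dose. SAP section 6 counts randomised and treated patients separately. Randomised but undosed patients are therefore foreseen.

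**Recovery.** SAP 9.2 tests time to clinical recovery on ITT Set – High Risk and then on the ITT Set, as the second and third key secondary endpoints. The time is the "elapsed time (in days) from the study drug administration to the earliest day satisfying condition for clinical recovery", computed as event or censoring date/time minus dosing date/time. Death, or early withdrawal for any reason, before Day 14 is censored at the scheduled Day 14 visit.

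**Secondary events.** SAP 9.3 lists, for example, "Proportion of patients with all-cause mortality (after study drug administration". The same bracket follows supplemental oxygen, ICU transfer, hospital admission and mechanical ventilation. These endpoints are analysed on both ITT and ITTI. Under SAP section 5, the denominator is every patient of the group in the population analysed.

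**Protocol.** Section 7.3.1 lists the same five endpoints without a dosing limit. Only rescue therapy is defined there from dosing. Section 7 says changes from the planned analyses will be documented in the SAP. SAP section 12 lists two: the wider ITTI definition and the removal of phenotype.

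**The concern.** The recovery tests are alpha-controlled, and the third key secondary endpoint is described as covering all randomised patients. For an undosed patient the SAP has a rule that would keep the patient (censor at Day 14) and a formula that cannot produce the time. A programmer would have to choose between dropping the patient, censoring at some improvised time, or starting the clock elsewhere. That choice should be written down before unblinding.

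In SAP 9.3 the stated rule can be applied, but it gives an unwanted answer. A patient who is randomised, not dosed, and then admitted, given oxygen or dies adds one to the ITT denominator and nothing to the numerator. An all-cause mortality figure for the ITT Set should not leave out a death because the infusion never took place. The limit narrows what the protocol lists, and the SAP does not record it as a change.

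**Working it through.** **1. The rules applied to a randomised patient who is never dosed**

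| Rule | Result |
|---|---|
| ITT membership (SAP 5.4.1) | Included |
| Recovery baseline (SAP 9.2, Screening or Day 1 checklist) | Can be determined |
| Recovery time (SAP 9.2, date/time minus dosing date/time) | Second term missing; no value |
| Censoring of early withdrawal (SAP 9.2) | Day 14 visit, but no origin to measure it from |
| Five event proportions (SAP 9.3) | In the denominator; event impossible |
| Disease status data (SAP 9.5; Protocol 6.1.2) | Monitored from consent, so an event can be on record |
| Primary and first key secondary endpoints (SAP 9.1, 9.2) | No after-dosing limit; unaffected |

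**2. The plan's own recovery power (SAP 5.2)**

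Inputs: 90% symptomatic at baseline, two-sided 5%. High-risk: 822 patients, ratio 1.5, 66% recovering. All randomised: 1300 patients, ratio 1.35, 65% recovering. Schoenfeld: power = Φ(√E/2 × ln(ratio) − 1.96).

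- High-risk: E = 822 × 0.90 × 0.66 = 488.3, power 99.4%. For 90% power, 256 events are needed.
- All randomised: E = 1300 × 0.90 × 0.65 = 760.5, power 98.5%. For 90% power, 467 events are needed.

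The stated power of at least 90% is reproduced for both tests.

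**3. Effect on the recovery tests**

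The documents give no undosed share, so 1%, 2% and 5% are assumptions. Patients concerned = N × 0.90 × share. Power if they are dropped uses E × (1 − share). The two columns for keeping them are log-rank simulations: 2,000 runs, exponential recovery times on a daily grid to Day 14, undosed patients equally likely in both arms. With the clock at randomisation, they recover at the placebo rate.

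| Test | Share | Patients concerned | Dropped | Kept, censored at Day 14 | Kept, clock at randomisation |
|---|---|---|---|---|---|
| High-risk | 1% | 7.4 | 99.4% | 99.2% | 99.3% |
| High-risk | 2% | 14.8 | 99.3% | 99.35% | 99.4% |
| High-risk | 5% | 37.0 | 99.2% | 98.8% | 98.65% |
| All randomised | 1% | 11.7 | 98.5% | 97.85% | 98.0% |
| All randomised | 2% | 23.4 | 98.4% | 98.15% | 98.05% |
| All randomised | 5% | 58.5 | 98.1% | 97.35% | 97.45% |

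The simulation error is about 0.4 points at the lowest value: √(0.9735 × 0.0265 / 2000) = 0.0036.

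**4. Effect on the event proportions**

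The plan gives no rates for the 9.3 endpoints. As an illustration, take its all-randomised composite rates, 5.5% and 2.5%. If undosed patients are automatic non-events, each rate is multiplied by (1 − share):

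- 1%: 5.45% and 2.48%, difference 2.97 points instead of 3.00
- 2%: 5.39% and 2.45%, difference 2.94 points
- 5%: 5.23% and 2.38%, difference 2.85 points

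Uncounted events = 1300 × share × rate. With the average rate of 4.0% and the placebo rate of 5.5% as a range:

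- 1%: 13 patients, 0.5 to 0.7 events
- 2%: 26 patients, 1.0 to 1.4 events
- 5%: 65 patients, 2.6 to 3.6 events

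The expected composite total is 650 × 0.055 + 650 × 0.025 = 52. Within these counts, deaths, ICU transfers and ventilation should be rarer still.

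**The case against.** The best defence is that the SAP excludes nobody. Its early-withdrawal rule can be read as keeping undosed patients to Day 14. The bracket in 9.3 also has an ordinary purpose: disease status is monitored from consent, so a start point is needed to keep pre-dose events out. Randomisation and dosing are both on Day 1, so few patients should be affected. Much of this stands, and it rules out several stronger readings.

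- **Undosed patients are removed from the recovery tests.** A reader might infer this from the formula, but no text says so. Their handling is undefined.
- **Their baseline symptoms cannot be determined.** SAP 5.5 says "The baseline value will be considered to be the last non-missing value before the study drug administration", which suggests a gap. For recovery, however, SAP 9.2 has its own rule: "The checklist at Screening or on Day 1 will be used to determine baseline and checklist from Day 2 will be used to determine clinical" … The entry condition, "For time to clinical recovery endpoints, patients who report at least one symptom at baseline will be included in the analysis", can therefore be decided without a dose.
- **Every secondary endpoint is cut off at dosing.** Checklist 2 scores carry no such limit. Fever duration is restricted by fever or antipyretic use on or before dosing, which is a different condition.
- **Rescue therapy departs from the protocol.** It does not; Protocol 7.3.1 defines it from dosing.
- **The 9.3 tables fail to reconcile with the primary composite.** An oxygen episode in an undosed patient could count in 9.1 and not in 9.3. But 9.3 uses all-cause mortality where the primary uses COVID-19 death, so full reconciliation was never intended.

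The defence leaves two gaps open. A censoring rule with no time origin cannot be run. Keeping pre-dose events out needs a start point, but for an ITT analysis randomisation provides one without losing undosed patients.

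**Conclusion.** The point holds for two places: the time origin in SAP 9.2 for ITT patients never dosed, and the after-dosing limit on five ITT event proportions in SAP 9.3, which the protocol does not contain and SAP section 12 does not list. The primary and first key secondary endpoints are not touched.

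The numerical effect is small. It rests on assumed undosed shares, since neither the number nor the balance between arms is given. Up to 5%, the lowest estimated recovery power is 97.35%, and an illustrative 3.00-point difference becomes 2.85. A reader might infer a loss of power or a confirmatory result at risk; the plan's figures do not support that. The reasons to act are that a confirmatory ITT test should have defined handling for every randomised patient, and that ITT deaths and admissions should all be counted.

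**What to change.** - **SAP 9.2:** for ITT patients never dosed, use randomisation (Day 1) as the time origin, and read the condition that symptoms change after dosing as after randomisation. The existing Day 14 censoring rule then applies to them. Dosed patients keep the present clock, and the recovery baseline needs no change.
- **SAP 9.3:** for the ITT analyses of oxygen, ICU transfer, all-cause mortality, admission and ventilation, count events from randomisation. Keep the dosing anchor for ITTI and for rescue therapy.
- **SAP section 12:** record the start point used for these endpoints.
- **Reporting:** give the number of randomised but undosed patients per arm.

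The cost is a few sentences. For dosed patients the 9.3 window moves by hours at most, because randomisation and dosing share Day 1. The documents do not say whether a clock time of randomisation is recorded; if only the date is held, a convention is needed.

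There are two downsides. A few more patients may count as not recovered. Their data after randomisation may also be incomplete: the return visit and telephone follow-up in SAP 4.1 are specified for withdrawal after dosing, although Protocol 4.2 is worded more broadly. The SAP should therefore say how missing outcomes in these patients are treated.
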